# **3 STATISTICAL ANALYSES**

# 3.1 GENERAL CONSIDERATIONS

This study is not intended to explicitly test a hypothesis. For primary and secondary efficacy endpoints, 95% CIs will be provided.

All efficacy endpoints based on radiological assessments of tumor burden (ie, ORR, DOR, PFS, and DCR) will be derived using the local radiologist's/Investigator's assessment.

In general, continuous data will be summarized using the number of observations available, mean, standard deviation, median, Q1, Q3, minimum, and maximum. Categorical and ordinal data will be summarized using the count and percentage of participants.

The baseline value is defined as the last available value before the first dose IMP.

The study cut-off for analysis of the primary endpoint for the Part 2 of the study, ORR, corresponds to the date on which all evaluable treated participants have had at least 2 postbaseline tumor assessments, experienced confirmed objective response, or have discontinued the study for any reason. This study cut-off can be up to approximately 16 weeks (12 weeks for 2 tumor assessments and 4 weeks for confirmation of response, if needed) after the last participant's first IMP administration.

The final study cut-off date for analysis of the secondary efficacy endpoints, which include DOR and PFS, will be 4 months after the cut-off date for the primary analysis. At that time, the primary analysis of ORR and DCR will also be updated.

# **Observation** period

The observation period will be divided into 4 segments:

- The **pre-treatment period** is defined as the period up to first IMP administration.
- The **on-treatment period** (ie, treatment-emergent (TE) period) is defined as the period from the first IMP administration to the last IMP administration +30 days.
- The **post-treatment period** is defined as the period from the end of the on-treatment period.

# 3.2 PRIMARY ENDPOINT(S) ANALYSIS

As it is a 2-part study, there are 2 primary endpoints: study-drug related DLTs at Cycle 1 and Cycle 2 in Part 1, and confirmed objective response as per RECIST 1.1 in Part 2.

# 3.2.1 Definition of endpoint(s)

## 3.2.1.1 Study-drug related DLT at Cycle 1 and Cycle 2

The primary safety endpoint is study-drug related DLTs during the DLT observation period (ie, from Cycle 1 Day 1 to Cycle 2 Day 14). The list of DLTs to be considered for the study is defined in Table 6 of the protocol. For analysis purposes, DLTs will be identified based on the Adverse Events (AEs) reported on the e-CRF DLT page during observation period in Part 1. Statistical analysis for DLTs is described in Section 3.6.2.

# 3.2.1.2 Confirmed objective response

The primary efficacy endpoint is confirmed objective response determined according to RECIST 1.1. A confirmed objective response is defined as a confirmed CR or PR as BOR.

The BOR will be derived according to RECIST 1.1 definitions (1, 2) based on the investigator's assessment. The BOR is the best overall response observed from the date of the first administration of IMP until documented disease progression, death, start of an anticancer therapy, or analysis cut-off date, whichever occurs first.

### 3.2.2 Main analytical approach

#### 3.2.2.1 Confirmed objective response

The primary efficacy analysis is based on the primary estimand for part 2 introduced in Section 1.2.1. This primary estimand is defined according to the following attributes:

- The primary efficacy endpoint is confirmed objective response (confirmed CR or PR as BOR) as per RECIST 1.1. based on the investigator's assessment as defined in Section 3.2.1.2.
- The treatment condition of interest is tusamitamab ravtansine loading dose Q2W in combination with ramucirumab.
- The analysis population is the participants from all-treated population (defined in Section 2) treated at the RD of tusamitamab ravtansine loading dose Q2W regimen (ie, excluding participants treated at the starting dose, if this differs from the RD).
- Intercurrent events:
  - The study intervention discontinuation intercurrent event will be handled with the treatment policy strategy. Confirmed objective response will be assessed based on tumor assessments regardless of study intervention discontinuation.
  - The further anticancer therapy (including further systemic anticancer therapies) intercurrent event will be handled with the "while not initiating further anticancer therapy" strategy. Confirmed objective response will be assessed based on tumor assessments done up to the time of initiation of further anticancer therapy.

• The population-level summary will be the ORR, defined as the rate of participants with confirmed objective response and 2-sided 95% CIs using the Clopper-Pearson method.

In the absence of confirmed objective response before the analysis cut-off date (taking into account the intercurrent event handling strategies), participants will be considered as non-responders, whatever the reason (including participants with missing or non-evaluable BOR).

# 3.2.3 Sensitivity analysis

No sensitivity analysis is planned in this study.

# 3.2.4 Supplementary analyses

Number (%) of participants within each BOR category, including not evaluable as per RECIST 1.1 and reason for being not evaluable will be provided on the subgroup of participants from the all-treated population treated at the RD (ie, excluding participants treated at the starting dose if this differs from the RD).

As a supplementary analysis, confirmed objective response as per RECIST 1.1 will also be summarized on the subgroup of participants from activity population (defined in Section 2) treated at the RD for tusamitamab ravtansine in a loading-dose Q2W regimen (ie, excluding participants treated at the starting dose if this differs from the RD). The same analytical approach as described above will be used.

In addition, the best relative tumor change from baseline, defined as the smallest relative tumor change from baseline (where tumor change at time t is the difference between sum of the longest diameters of the target lesions at time t and baseline, resulting in a negative value in case of decrease), will be summarized using a waterfall plot on the participants on the all-treated population treated at the RD (ie, excluding participants treated at the starting dose if this differs from the RD). A swimmer plot will also be provided reporting the duration of treatment for all participants with their overall response and some baseline characteristics. This plot will differentiate responders from non-responders. In addition, a spider plot will also be provided reporting the tumor change from baseline over the time.

# 3.3 SECONDARY ENDPOINT(S) ANALYSIS

The secondary endpoints detailed in this section are the duration of response, the progression-free survival and the disease control rate. Other secondary endpoints analyses are defined in Section 3.6.2 (AE, SAE), Section 3.6.3.1 (laboratory abnormalities), Section 3.7.1.1 (PK) and Section 3.7.1.2 (immunogenicity).

# 3.3.1 Key/Confirmatory secondary endpoint(s)

No key/confirmatory endpoint is defined.

# 3.3.2 Supportive secondary endpoint(s)

## 3.3.2.1 Definition of endpoints

#### 3.3.2.1.1 Duration of response

DOR is defined as the time from the date of first initial occurrence of the confirmed CR or PR to the date of first documentation of objective progressive disease according to RECIST 1.1 (1, 2) or death due to any cause, whichever occurs first.

### 3.3.2.1.2 Progression-free survival

PFS is defined as the time from the date of the first administration of IMP to the date of the first documentation of objective progressive disease according to RECIST 1.1 (1, 2) or death due to any cause, whichever occurs first.

### 3.3.2.1.3 Disease control rate

The DCR is estimated by dividing the number of participants with confirmed objective response or SD (CR or PR or SD as BOR), determined according to RECIST 1.1, by the number of participants from the analysis population.

### 3.3.2.2 Main analytical approach

#### 3.3.2.2.1 Duration of response

DOR analysis is based on an estimand defined according to the following attributes:

- The endpoint is duration of response as defined in Section 3.3.2.1.
- The treatment condition of interest is tusamitamab ravtansine loading dose Q2W in combination with ramucirumab.
- The analysis population is the participants from the all-treated population (defined in Section 2) treated at the RD of tusamitamab ravtansine in a loading-dose Q2W regimen (ie, excluding participants treated at the starting dose if this differs from the RD) limited to participants who achieved a confirmed objective response.
- Intercurrent events:
  - The study intervention discontinuation will be handled with the treatment policy strategy. DOR will be assessed based on tumor assessments regardless of study intervention discontinuation.
  - The further anticancer therapy (including further systemic anticancer therapies) intercurrent event will be handled with the hypothetical strategy. DOR will be assessed based on tumor assessments had a further anticancer therapy not been taken. DOR will be assessed based on tumor assessments up to the time of initiation of further anticancer therapy.

- Two or more consecutive missing/unevaluable tumor assessments immediately before documented PD or death will be handled with the hypothetical strategy. DOR will be assessed based on tumor assessments had 2 consecutive tumor assessments not been missed immediately before documented PD or death. DOR will be assessed based on tumor assessments up to the last evaluable tumor assessment documenting no progression.
- The population-level summary will include the median DOR and associated 95% CI from Kaplan-Meier methods.

In the absence of documented disease progression or death before the analysis cut-off date (taking into account the intercurrent event handling strategies), DOR will be censored at the date of the last evaluable tumor assessment (not showing documented disease progression) performed before the analysis cut-off date.

# 3.3.2.2.2 Progression-free survival

PFS analysis is based on an estimand defined according to the following attributes:

- The endpoint is progression-free survival.
- The treatment condition of interest is tusamitamab ravtansine loading dose Q2W in combination with ramucirumab.
- The analysis population is the participants from the all-treated population (defined in Section 2) treated at the RD of tusamitamab ravtansine in a loading-dose Q2W regimen (ie, excluding participants treated at the starting dose if this differs from the RD).
- Intercurrent events:
  - The study intervention discontinuation will be handled with the treatment policy strategy. PFS will be assessed based on tumor assessments regardless of study intervention discontinuation.
  - The further anticancer therapy (including further systemic anticancer therapies) intercurrent event will be handled with the hypothetical strategy. PFS will be assessed based on tumor assessments had a further anticancer therapy not been taken. PFS will be assessed based on tumor assessments up to the time of initiation of further anticancer therapy.
  - Two or more consecutive missing/unevaluable tumor assessments immediately before documented PD or death will be handled with the hypothetical strategy. PFS will be assessed based on tumor assessments had 2 consecutive tumor assessments not been missed immediately before documented PD or death. PFS will be assessed based on tumor assessments up to the last evaluable tumor assessment documenting no progression.
- The population-level summary will include:
  - Kaplan-Meier estimates of the 25th, 50th, and 75th percentiles and their associated 95% CIs using a log-log transformation of the survival function and the method of Brookmeyer and Crowley.

- Number (%) of participants at risk as well as the probabilities of being event-free at least at 3, 6, 9, and 12 months with 95% CIs using the Kaplan-Meier method and a log-log approach based on a normal approximation following the Greenwood's formula.
- Kaplan-Meier curve including the number of participants at risk at key time points.

In addition, the number (%) of participants with an event and the type of event (documented disease progression or death without documented disease progression) and the number (%) of censored participants and reason for censoring (no baseline tumor assessment, no evaluable post-baseline tumor assessments, alive without documented disease progression, event occurred after two or more non-evaluable tumor assessments, or initiation of further anticancer therapy) will be analyzed.

In the absence of documented disease progression or death before the analysis cut-off date (taking into account the intercurrent event handling strategies), PFS will be censored at the date of the last evaluable tumor assessment (not showing documented disease progression) performed before the analysis cut-off date, or at the date of the first administration of IMP (Day 1) if no PFS event (documented disease progression or death) and no baseline tumor assessment or no evaluable postbaseline tumor assessment has been done.

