Participants with a global deterioration of health status requiring discontinuation of treatment without objective evidence of disease progression at that time should be reported as “symptomatic deterioration”. Every effort should be made to document objective progression even after discontinuation of treatment. Symptomatic deterioration is not a descriptor of an objective response: it is a reason for stopping study therapy.

The objective response status of such participants is to be determined by evaluation of target and non-target disease. For equivocal findings of progression (eg, very small and uncertain new lesions; cystic changes or necrosis in existing lesions), treatment may continue until the next scheduled assessment. If at the next scheduled assessment, progression is confirmed, the date of progression should be the earlier date when progression was suspected.

Duration of response

The duration of overall response is measured from the time measurement criteria are first met for CR/PR (whichever is first recorded) until the first date that recurrent or PD is objectively documented (taking as reference for PD the smallest measurements recorded on study).

The duration of overall CR is measured from the time measurement criteria are first met for CR until the first date that recurrent disease is objectively documented.

Duration of stable disease

Stable disease is measured from the start of the treatment until the criteria for progression are met, taking as reference the smallest sum on study (if the baseline sum is the smallest, this is the reference for calculation of PD).

Reproduced from:

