# 2 ANALYSIS POPULATIONS

The following populations for analyses are defined:

Population	Description		
Prescreened	All participants who signed the prescreening informed consent for CEACAM5 assessment of their biopsy.		
Screened	All participants who signed the screening informed consent for study participation.		
Enrolled	Participants from screened population who have been allocated to intervention regardless of whether the intervention was received or not.		
All-treated	All enrolled participants exposed to the study treatment, regardless of the amount of treatment administered. All safety analyses will be performed on this population, which is also the primary population for analysis of all efficacy parameters.		
DLT-evaluable (Part 1)	All enrolled participants who received 2 cycles with at least 80% of the intended dose for both tusamitamab ravtansine and ramucirumab at each of the first 2 infusions. Any participant who experienced a DLT during that period will also be DLT-evaluable.		
Activity	All-treated participants who have measurable disease at study entry and at least 1 postbaseline evaluable tumor assessment. Participants with no postbaseline evaluable tumor assessment but with an early clinical progression or who died from disease progression will also be included in this set. This population is the secondary population for analysis of efficacy parameters.		
Pharmacokinetic (PK)	All participants from the all-treated population with at least 1 postbaseline PK concentration (whatever the cycle and even if dosing is incomplete) with adequate documentation of dosing and sampling dates and times.		
ATA	All participants from the all-treated population with at least 1 postbaseline ATA result (negative, positive, or inconclusive).		
Population without trial impact	All treated participants:		
(disruption) due to COVID-19	
 
without any critical or major deviation related to COVID-19
 
		
	
 
and who did not permanently discontinue treatment due to COVID-19
 
		
	
 
and who did not permanently discontinue study due to COVID-19.
 
		

Table 4 - Populations	for analyses
-----------------------	--------------

In practice, a participant will be included in the enrolled population if the question "Will the subject continue in the treatment phase?" has been answered "Yes" in the "Completion of screening phase" e-CRF page.

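### Participants who progress clinically and switch therapy with no evaluable scan are censored at Day 1 in PFS, and no supplementary analysis would show the effect

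*SAP*

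**What the plan says.** **PFS event.** SAP 3.3.2.1.2 measures PFS to the "first documentation of objective progressive disease according to RECIST 1.1" or death. Clinical progression alone does not qualify. Protocol Appendix 13 agrees: "Symptomatic deterioration is not a descriptor of an objective response: it is a reason for stopping study therapy".

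**Further anticancer therapy.** SAP 3.3.2.2.2 uses a hypothetical strategy: "PFS will be assessed based on tumor assessments up to the time of initiation of further anticancer therapy". Protocol 9.3.3.2 likewise censors anyone who starts a new therapy before a PFS event, so a later progression or death does not count.

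**Censoring date.** This is the last evaluable scan, "or at the date of the first administration of IMP (Day 1) if no PFS event" has occurred and "no evaluable postbaseline tumor assessment has been done". Protocol 9.3.3.2 has the same Day 1 rule.

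**Other endpoints.** Under SAP 3.2.2.1 and 3.3.2.2.3, a participant with a missing or non-evaluable best response is a non-responder for ORR and a failure for DCR. The activity population (SAP 2) names this group: "Participants with no postbaseline evaluable tumor assessment but with an early clinical progression or who died from disease progression will also be included".

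**Checks planned.** SAP 3.2.3 plans no sensitivity analyses. ORR and DCR each have a supplementary analysis on the activity population; PFS has none. SAP 3.3.2.2.2 tabulates censoring reasons, including lack of an evaluable postbaseline scan and start of further anticancer therapy, but not clinical progression.

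**The concern.** Put together, these rules give one group of treatment failures no weight in PFS. A participant who deteriorates before the first scheduled scan at week 6, stops, and starts another therapy with no evaluable scan has no event and no scan date. Follow-up is set to zero.

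Kaplan-Meier estimation assumes that censored participants have the same outlook as those who stay at risk. Here the reason for leaving is worsening disease, so the censoring is informative, and relative to counting these participants as failures it can only raise the curve. With a single arm there is no control group subject to the same rule, and with about 32 participants a few cases would visibly move the median.

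The planned tables would not reveal this. Such a participant fits two of the listed censoring reasons, and neither says that the disease had clinically progressed.

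**Working it through.** **Inputs**
- n = 32: the target at the recommended dose (Protocol 9.1; SAP 4), made up of 26 Part 2 participants plus 6 from Part 1, 26 + 6 = 32. PFS is analysed on all participants treated at that dose, so the actual n may differ.
- k: the number censored at Day 1 after clinical progression and a switch. Neither document gives a rate, so k = 0 to 3 is an assumption.
- Median PFS under the SAP rule: an assumption, because the plan states none and there is no planned PFS figure to reproduce. I use 4.4 months, which Protocol 2.1 quotes for ramucirumab plus paclitaxel, and try 2.9 (quoted there for paclitaxel alone) and 6.0. Survival is taken as exponential: S(t) = 0.5^(t/m).

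**Step 1: the factor.** Under the SAP rule the k participants leave at time 0, so the curve is built on the other n − k. If they are instead events before any other event or censoring, the curve first drops to (n − k)/n and then follows the same steps:

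S_event(t) = (1 − k/n) × S_SAP(t).

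The SAP curve is therefore higher by 1/(1 − k/n): 1.032 for k = 1, 1.067 for k = 2 and 1.103 for k = 3. A simulation with 6-weekly scans and administrative censoring gave ratios of 3-month rates of 0.9688, 0.9375 and 0.9062, matching 1 − k/32.

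**Step 2: the median.** Setting (1 − k/n) × 0.5^(t/m) = 0.5 gives t = m × log2[(1 − k/n)/0.5]. For k = 1 and m = 4.4: 4.4 × log2(0.96875/0.5) = 4.4 × 0.954 = 4.20 months.

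| k | Median if counted, m = 2.9 | m = 4.4 | m = 6.0 | 3-month PFS, m = 4.4 | 6-month PFS, m = 4.4 |
|---|---|---|---|---|---|
| 0 | 2.90 | 4.40 | 6.00 | 62.3% | 38.9% |
| 1 | 2.77 | 4.20 | 5.73 | 60.4% | 37.6% |
| 2 | 2.63 | 3.99 | 5.44 | 58.4% | 36.4% |
| 3 | 2.49 | 3.78 | 5.15 | 56.5% | 35.2% |

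**Step 3: who is left after the end-of-treatment scan.** The synopsis places the end-of-treatment visit before any new anticancer therapy if that comes first. Protocol 8.1 asks for a scan at that visit unless imaging was done in the preceding 4 weeks. The baseline scan may be close to Day 1, and the text does not limit the exemption to postbaseline imaging. A participant who fails within the first cycles can therefore be exempt. Others remain if the scan is missed or not evaluable. A readable scan without progression moves the censoring to that scan, not Day 1. A death before new therapy is an event, unless two or more assessments were missed just before it.

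**The case against.** The strongest reply is that the plan already makes this group small. Besides the end-of-treatment scan, Protocol Appendix 13 asks sites to try to document progression objectively after treatment stops, and SAP Appendix 4 uses unscheduled scans. This stands: true early progressors should often become documented events. It narrows the group without closing it, and the fastest progressors are the most likely to fall within the exemption.

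Four stronger readings are tempting, and the documents do not support them:
- *PFS is overstated.* This holds only if such participants occur.
- *The SAP contradicts itself.* PFS is not analysed on the activity population. That definition only includes these participants; they fail ORR and DCR because any missing or non-evaluable best response does. The difference is between endpoints, not within one analysis.
- *Counting clinical progression gives the correct PFS.* It answers a different question. RECIST-only PFS was prespecified in the protocol and fits Appendix 13.
- *The bias will distort a historical comparison.* None is planned, and the documents do not show how the cited trials censored.

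It is also fair to say that sampling error is larger than the shift. At 38.9% and n = 32, a simple binomial 95% half-width is 1.96 × √(0.389 × 0.611/32) = 0.169, about 17 points, against 3.7 points at 6 months for k = 3. That limits the importance of the point, but the interval does not cover a shift that always goes one way.

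**Conclusion.** The point holds in conditional form. The rule censors at Day 1 a participant who clinically progresses and switches therapy with no evaluable postbaseline scan, and no planned PFS analysis shows what that does. The direction is certain once k is at least 1. At n = 32 and an assumed SAP-rule median of 4.4 months, each such participant is worth about 0.2 months of median and 1/32 = 3.1% of the curve's height. Zero cases means zero effect.

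The size rests on the assumed k, the assumed median, the exponential form, and these events falling before all others. PFS is a descriptive secondary endpoint with no hypothesis test, so no error rate is affected. This is a cheap improvement to reporting and does not invalidate the planned analysis.

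**What to change.** Leave the main PFS analysis as it is. Add to SAP 3.3.2.2.2:

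1. One supplementary Kaplan-Meier analysis of PFS on the same population. Start of further anticancer therapy, or treatment discontinuation for clinical progression, without previously documented progression, counts as an event at that date (the earlier date if both occur).
2. One sentence on how clinical progression is identified, for example from the recorded reason for treatment discontinuation. Neither document defines the early clinical progression used for the activity population, so the sentence would serve there too.
3. A count of participants censored at Day 1, by reason, with clinical progression as its own category.

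The supplementary analysis also turns later switchers without documented progression into events, so its gap from the main result will not come from the Day 1 group alone. The count in item 3 lets a reader separate the two.

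Cost: one extra Kaplan-Meier run and one table row, on data already collected (reasons for discontinuation, further therapy). The supplementary PFS may be slightly less favourable, and its event is more subjective in an open-label, investigator-assessed study, which is why it should stay supplementary.
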